The primary asthma morbidity outcomes will be FEV1 and control (ACQ scores); the primary measure of NO metabolism will be L-arginine/ADMA ratio. All analyses will compare four groups: 1) obese with late onset asthma; 2) obese with early onset asthma; 3) non-obese with late onset asthma; and 4) non-obese with early onset asthma. First, we will compare the levels of plasma L-arginine, ADMA, L-arginine/ADMA ratios, and arginase among these groups, at each time point using the Kruskal-Wallis test. The Wilcoxon signed-rank test will be used to compare levels of NO metabolism biomarkers in periods without vs. during asthma attacks. The analysis will involve longitudinal assessment of asthma morbidity measures across four time points (0, 6, 12, and 18 months). We hypothesize that both time-varying covariates (e.g., NO metabolism biomarkers) assessed at the four time points and time-invariant covariates (e.g., early vs. late asthma onset) will predict asthma morbidity assessed at these time points (Figure 1). We also hypothesize potential lagged effects of covariates at earlier time points. As a first step, we will identify the measurement model for the latent variables at each time point using confirmatory factor analysis. Specifically, we will create latent variables representing random effects intercepts and slopes for NO metabolism (NOt0, NOt6, NOt12 and NOt18; where t0 represents baseline NO metabolism biomarkers) and asthma morbidity measures (AMt0, AMt6, AMt12 and AMt18; e.g., FEV1 at baseline, 6, 12, and 18 months). We will estimate slope and intercept parameters using a Weighted Least Squares Mean-Variance adjusted (WLSMV) estimator, which provides robust estimates for complex models with modest sample sizes and can be employed with dichotomous, ordinal, and/or continuous endogenous variables. We will test this measurement model for absolute fit using Chi-square and RMSEA statistics. In addition, we will consider adjusting the model based on modification indices to improve the overall fit.

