Next, an overall unconditional model will be fitted to identify the growth trajectory across time. To that end, we will fit a growth function for NO metabolic biomarkers and asthma morbidity (e.g., FEV1) using linear, quadratic, and unstructured models. Relative model fit will be evaluated based on various indices of exact and close fit:  $\chi^2$  (>.05), the comparative fit index (CFI>.97), the Tucker-Lewis fit index (TLI>.97), the root mean squared error of approximation (RMSEA<.05), and the weighted root mean square residual when using WLSMV (WRMR<.90). The most parsimonious model with the best fit will be retained. Finally, we will fit the full structural model, including the hypothesized relationships. For example, obesity and age of onset will be included as a predictor of NO metabolism-related pathways as well as asthma morbidity. Because we hypothesize that NO metabolism-related pathways are primarily important for obese patients with late onset asthma, we will include an interaction term between obesity and age of asthma onset. The model will also control for sex, age, comorbidities (including OSA), depression, allergic sensitization, and other key baseline covariates. To address the possible mediational effects of NO metabolism-related pathways, we will fit models to estimate both direct and indirect effects, first separately, and then combined. Lagged effects of the time- varying predictors, as well as the effects of the latent growth variables themselves (intercept, slope, and their random effects) will be evaluated as potential mediators (i.e., NO metabolism biomarkers) of the effects of obesity and age of onset on asthma morbidity. We will also be able to compare models of complete vs. partial mediation by comparing constrained models (direct effects constrained to zero) with unconstrained models that allow for partial mediation. Relative fit, as well as estimates of effect size will be calculated, along with Sobel tests and Monte Carlo confidence intervals to evaluate the mediational hypotheses. As indicated above, the interrelationships between gender, obesity, and asthma morbidity is complex, thus, we will explore the potential modifying effects of gender. We will also conduct sensitivity analyses in which we test different thresholds for the definition of good medication adherence (≥70%, 60%, 50%). Once the final model is fitted, we will repeat the analyses freeing the parameters to differ by gender. Comparing these models to a model in which the differential effects of gender are constrained will provide valuable insight into the possible role of

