
gender in the hypothesized effects.

[figure not shown]
**Note:** In addition to data from the 4 scheduled time points, we will also obtain data when patients have asthma exacerbations. Because LGCM is limited in its ability to model effects in which time points are not common throughout patients (as anticipated for exacerbation data), we will use more flexible hierarchical growth models (e.g., linear mixed models or generalized linear mixed models) as needed to explore these data points.

**Aim 2.** Evaluate the interrelation between obesity- and asthma-related illness beliefs, and the impact of cognitive function, on patients' management of these conditions over time: For asthma, we will compare electronic (primary outcome) and self-reported (secondary outcome) adherence to medications according to obesity/age of onset categories using a chi-square test. For obesity, primary outcomes will be the Connor Diet Habit Survey scores for diet and accelerometer data for exercise. Secondary analyses will assess other SMB.

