We will use LGCM to examine the interrelationships between asthma- and obesity-related beliefs and self-management of these conditions over time (Figure 4). Latent variables to be investigated include: 1) cognition, as measured by the battery described above; 2) asthma beliefs; 3) obesity beliefs. Asthma and obesity beliefs will constitute a latent variable consisting of two constructs: a) disease beliefs (measured with the IPQ) and b) medication/diet/exercise beliefs (measured with the BMQ); and 3) asthma and obesity SMB, including time-variant medication adherence (electronic and self-report measures following each study time point), diet, exercise and other SMB. We will use LGCM to predict the effects of obesity on these latent behavioral constructs. We will be able to examine the direct and indirect pathways from obesity to cognitive functioning and illness beliefs, to asthma and obesity SMB (intercept, slope, as well as their random effects). We will assess the potential influence of cognition and illness beliefs on SMB separately then test a full model, predicting SMB once individual contributions are identified. As in Aim 1, we will estimate both direct and indirect effects, as well as partial vs. complete mediation. We will include covariates as above. Integrating Biological and Behavioral Pathways: Finally, we will employ LGCM to characterize the interrelation and relative contribution of biological and behavioral pathways linking obesity and asthma morbidity (Figure 1). In addition to the time-variant relationships between SMB and biological markers, we will also explore the possibility of time-lagged relationships between biological markers and SMB. For example, we will assess if SMB at time 1 predict L-arginine/ADMA ratios at time 2, and vice-versa. Comparison of model fit among these lagged analyses will yield critical new data to elucidate the complex interplay between biology and behavior in the maintenance of asthma morbidity. The model will control for other confounders as specified above.

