**Missing Data:** For data missing at random (e.g., data entry errors), we will use multiple imputation methods with PROC MI and PROC MIANALYZE in SAS. For the outcome assessments, we cannot assume data are missing at random, but we will consider pattern-mixture methods to adjust for an occasional missed point in subjects who complete subsequent follow-up. **Power Calculation:** Power calculations for LGCM and sample size based were based on published methods. Effect size in this approach is defined as a null and alternative hypothesis value of the RMSEA index, which we hypothesize to be 0.05 (adequate fit) and 0.03 (good exact fit), respectively. Power in SEM can be conceptualized as a function of sample size and the number of parameters to be estimated in the model, relative to the information provided in the overall variance-covariance matrix of the observed variables. The estimated power is based on a proposed sample size of 400 with an 80% follow-up rate. For Aim 1, the proposed model involves 14 latent variables across all time points, and 34 observed underlying variables, yielding estimated power >0.80 for an average effect of 0.10 with an alpha of 0.05. For the model in Aim 2, there are 13 latent variables (not including the six separate indicators of cognition) and 18 observed variables, yielding >0.80 power for average effects of 0.15. Overall, despite the challenges of estimating *a priori* power for SEM approaches, especially those involving growth models, we believe the proposed study will be adequately powered to address the research aims.

**Aim 3.** Develop and pilot test three theory-based modules that integrate counseling for asthma and obesity to promote better SMB, including self-monitoring, adherence to asthma medications, and lifestyle changes for weight loss: **Overview:** We will script messages aimed to counter beliefs linked to low adherence to asthma and obesity SMB and to support those that promote better SMB. We will incorporate these messages in 3

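### The Aim 2 group comparison of the primary adherence outcome uses chi-square, which forces an unstated cut-point and loses roughly a third to a half of the information in that comparison

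*SAP*

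**What the plan says.** - **The test.** SAP, Aim 2: "we will compare electronic (primary outcome) and self-reported (secondary outcome) adherence to medications according to obesity/age of onset categories using a chi-square test". That sentence gives no cut-point and no time point.
- **The groups.** SAP, Aim 1 defines the four obesity/age-of-onset groups: "All analyses will compare four groups: 1) obese with late onset asthma; 2) obese with early onset asthma", then the two matching non-obese groups. It compares the plasma biomarkers across them with Kruskal-Wallis at each time point.
- **The thresholds.** The Aim 1 text plans "sensitivity analyses in which we test different thresholds for the definition of good medication adherence", and names at least 70%, 60% and 50%. No threshold is marked as primary.
- **The self-report scale.** SAP, Pilot RCT Procedures, lists MARS as the medication adherence measure and analyses it by t-test or Wilcoxon test, that is, as a score.
- **The growth model.** The Aim 2 latent growth curve model (LGCM) includes "asthma and obesity SMB, including time-variant medication adherence (electronic and self-report measures following each study time point), diet, exercise and other SMB", with the Aim 1 covariates. The estimator, described under Aim 1, "can be employed with dichotomous, ordinal, and/or continuous endogenous variables". The form in which adherence enters is not stated.

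**The concern.** Electronic adherence is the primary outcome for asthma self-management in Aim 2, and this sentence is the only place where it is explicitly compared across the four groups. A percentage and a scale score must both be turned into good or poor adherence before a chi-square can be run. Two things are at stake. The comparison loses power to detect a difference between groups. And because no primary threshold is fixed, the answer can depend on a cut chosen after the data are seen. The SAP has a test in use for the same four groups that needs no cut.

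**Working it through.** **1. The plan's own figure.** The documents give no power, effect size or adherence distribution for this comparison. The only Aim 2 power statement is for the LGCM: above 0.80 for average effects of 0.15. "The estimated power is based on a proposed sample size of 400 with an 80% follow-up rate", so N = 400 × 0.80 = 320. It rests on RMSEA null and alternative values, "which we hypothesize to be 0.05 (adequate fit) and 0.03 (good exact fit), respectively". It cannot be reproduced, because the model degrees of freedom (df) are not given. With the non-central chi-square (lower tail, alpha 0.05), power of 0.80 needs at least 99 df at N = 320 or 71 at N = 400. The 18 observed variables allow at most 18 × 19 / 2 = 171 df from covariances, so the claim is possible but unconfirmed. It says nothing about the chi-square comparison.

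**2. Efficiency of a cut.** Assume normal adherence, a small shift between groups and two categories, with a proportion p on one side of the cut. The efficiency relative to comparing means is φ(z_p)² / [p(1 − p)].

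| Split | φ(z_p)² | p(1 − p) | Efficiency | Loss |
|---|---|---|---|---|
| 50/50 | 0.1592 | 0.25 | 0.637 | 36% |
| 35/65 | 0.1372 | 0.2275 | 0.603 | 40% |
| 25/75 | 0.1010 | 0.1875 | 0.539 | 46% |
| 20/80 | 0.0784 | 0.16 | 0.490 | 51% |
| 10/90 | 0.0308 | 0.09 | 0.342 | 66% |

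Matching the continuous comparison would take 1/0.637 = 1.57 times the sample at 50/50 and 1/0.539 = 1.86 times at 25/75.

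Kruskal-Wallis has efficiency 3/π = 0.955 for normal data. Against it the loss is 1 − 0.637/0.955 = 33% at 50/50 and 1 − 0.539/0.955 = 44% at 25/75.

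**3. In terms of power.** A 3-df test at alpha 0.05 has 80% power at non-centrality 10.90. Multiplying by the efficiency gives 6.94 at 50/50 and 5.87 at 25/75, which is power of 59% and 51%.

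**4. Finite-sample check.** Assume 80 per group (320/4, equal groups), normal data and one group 0.45 SD lower. The effect size is chosen for illustration. In 4,000 simulated trials Kruskal-Wallis power was about 82%. Chi-square power was about 61%, 53% and 45% when 50%, 35% and 25% of the other groups were classed as good. A repeat with 8,000 trials agreed within about one percentage point.

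**5. Other distributions.** With assumed beta-shaped adherence (mean 0.38 to 0.60) cut at 50%, 60% or 70%, the loss was 33–59% against a comparison of means and 35–59% against Kruskal-Wallis.

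**6. Dependence on the cut.** In the simulations of step 4 the three cuts disagreed on significance in 42–44% of trials. With no true difference, at least one of the three was significant in about 11% of trials, against a nominal 5%.

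**The case against.** The strongest reply is that the chi-square is only an unadjusted description. The SAP overview says that LGCM will test the Aim 1 and Aim 2 hypotheses, and the Aim 2 model takes adherence over time with covariates. This largely stands. A reader might infer that Aim 2 as a whole loses this information, or ignores covariates and repeated measurements; the documents do not support that. What remains is that the LGCM text names effects of obesity and does not mention age of onset, so the four-group comparison of adherence is explicit only in the chi-square sentence.

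The threshold analyses are named in advance, which partly answers the worry about the cut. But they sit under Aim 1, and sensitivity thresholds do not say which result is primary. The SAP also refers back to text not in this document, so the measure and its cut may be defined there. The percentage scale is an inference from the thresholds, though a strong one.

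A reader might also fault the chi-square for not testing obese late-onset patients against the rest. That hypothesis is stated for nitric oxide metabolism in Aim 1, and not for adherence.

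Percent with good adherence is easy to read, and that is a fair reason to keep reporting it. It is not a reason to make it the test.

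**Conclusion.** The point holds for the stated four-group comparison of electronic and self-reported adherence. The chi-square forces categories on measures that the SAP elsewhere treats as a percentage and a score, and no primary cut is given. The loss is roughly one third to one half of the information: 36% at a 50/50 split and 46% at 25/75 for normal data and a small shift, and more at extreme splits. A reader might take 36–46% as a property of this plan. It is not, because the documents state neither the distribution nor the proportion who will be classed as adherent. The direction of the loss does not depend on normality. The change is worth making because a primary outcome is affected and the remedy costs almost nothing, but the Aim 2 growth model is untouched by it.

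**What to change.** In the Aim 2 text of the SAP:

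- Define the electronic measure and its scale.
- Replace the chi-square with a Kruskal-Wallis comparison of electronic adherence and of the MARS score across the four groups at each time point, as Aim 1 does for the biomarkers. State in advance which time point carries the primary comparison.
- Leave the adjusted longitudinal analysis to the growth model, and say that adherence enters it as continuous.
- Keep the 70%, 60% and 50% tables, with chi-square, as descriptive or supportive.
- Fix the test now, so that the data do not choose it, and do not add an obese late-onset contrast for adherence.

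The cost is a few lines of SAP wording and no new data. The primary comparison becomes slightly harder to read than a percentage of adherent patients, but the retained tables still give that figure.

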Obesity and Asthma: Unveiling Metabolic and Behavioral Pathways

Statistical Analysis Plan

PI: [name], DrPH

NCT04113746

Document Date: 8-12-2015

**Data Analyses:** We will obtain a HIPAA waiver to use de-identified data to compare non-respondents and those lost to follow-up to study participants by age, gender and ethnicity. **Factor Structure of Measures:** We will examine the factor structure of key measures (e.g., MARS) and the multi-component structure of the IPQ and BMQ. **Measurement Invariance:** We will determine whether the key measures are invariant across language using multiple indicator multiple cause models. We will use the chi-square test, ANOVA, or the Kruskal Wallis test to compare the baseline characteristics of obese vs. non-obese patients with early onset and late onset asthma, as appropriate. **Overview:** We will employ latent growth curve modeling (LGCM) approaches using MPLUS 7.3 software to test Aims 1 and 2 hypotheses. LGCM leverages the analytical power of structural equation modeling (SEM) for the intensive analysis of longitudinal data. Similar to classic SEM, LGCM allows for the examination of complex models including those that posit mediation and moderation, as proposed here. Before conducting analyses, we will examine the distribution of dependent variables and, as appropriate, consider transformations (e.g., log, Box-Cox) to reduce non-normality in continuous variables.

**Aim 1.** Compare the longitudinal relationship between L-arginine/ADMA balance and morbidity (lung function, asthma control, acute resource utilization, and quality of life) between obese adults with late onset asthma vs. (1) obese adults with early onset asthma and non-obese asthmatics with early (2) or late (3) onset disease:

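### The SAP declines to assume outcomes are missing at random, but commits to no handling and no sensitivity analysis for FEV1 and ACQ after permanent loss to follow-up

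*SAP*

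**What the plan says.** The Missing Data section of the SAP reserves multiple imputation for data missing at random, with data entry errors as its example. It then sets outcomes apart: "For the outcome assessments, we cannot assume data are missing at random". What it offers for them is this: "we will consider pattern-mixture methods to adjust for an occasional missed point in subjects who complete subsequent follow-up".

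The Power Calculation section expects some loss: "The estimated power is based on a proposed sample size of 400 with an 80% follow-up rate".

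Under Aim 1, FEV1 and ACQ are the primary morbidity outcomes, measured at 0, 6, 12 and 18 months. The estimator is named: "We will estimate slope and intercept parameters using a Weighted Least Squares Mean-Variance adjusted (WLSMV) estimator". A later fit criterion is worded "the weighted root mean square residual when using WLSMV", which leaves room for another estimator. Neither place says how incomplete records enter the model. In the full structural model "obesity and age of onset will be included as a predictor of NO metabolism-related pathways as well as asthma morbidity", and an obesity by onset interaction is added.

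**The concern.** Pattern-mixture methods can handle outcomes that are not missing at random, so the SAP names a suitable class of method. It then limits that class to gaps in patients who come back. Patients who never return are the ones whose unseen values are hardest to predict, and they fall outside its stated scope.

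What is at stake is the later course of FEV1 and ACQ, meaning the 12- and 18-month means and the growth slopes, and any direct obesity or onset effect on that course. If patients with worse (or better) control leave, those means shift. If they leave at different rates or for different reasons across the four groups, the group contrasts shift too. The plan has no analysis that would show a reader how far a conclusion depends on this.

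**Working it through.** **1. The plan's own figures.** 400 x 0.80 = 320 followed; 400 - 320 = 80 not followed. The SAP does not say how many of the 80 are permanent losses, so 80 is an upper bound. The stated Aim 1 power (>0.80, RMSEA 0.05 versus 0.03, alpha 0.05) needs at least 99 degrees of freedom at N = 320, or 71 at N = 400. The degrees of freedom are not given, but 34 observed variables supply 34 x 35 / 2 = 595 variances and covariances. The figure is therefore plausible and is not disputed here.

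**2. Does any other text cover outcomes after permanent loss?**
- Multiple imputation (SAP, Missing Data): for data missing at random; the next sentence takes outcomes out.
- Comparison of those lost (SAP, Data Analyses): descriptive, on age, gender and ethnicity only.
- Mixed models (SAP, Note after Aim 1): "we will use more flexible hierarchical growth models (e.g., linear mixed models or generalized linear mixed models) as needed to explore these data points". The points meant are exacerbation data, not missed scheduled visits.
- Sensitivity analyses (SAP, Aim 1): these vary the adherence threshold.
- Withdrawal (Protocol, text before section 4): data already collected are kept unless the patient asks for destruction. Earlier visits survive, but nothing says how they inform later ones.

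**3. Size of the bias in a mean.** The documents give no dropout mechanism, so these inputs are assumed: four visits, flat true course, within-person correlation 0.5-0.7, log-odds of dropout 0.5-1.0 per SD of the outcome, 20% cumulative loss by month 18. Available-case estimates stand in for WLSMV. Error in the 18-month mean:

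| Dropout follows | Available case | Maximum likelihood |
|---|---|---|
| Last observed value | 0.05-0.13 SD | 0.00 SD |
| Unseen current value | 0.07-0.15 SD | 0.02-0.07 SD |
| Nothing (completely at random) | 0.00 SD | 0.00 SD |

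The available-case error in linear change is of the same size. Adjusting for baseline covariates that explain 10-30% of variance still leaves 0.03-0.10 SD (correlation 0.6, last-value dropout). Month 0 precedes dropout, so the baseline level is not affected in this set-up.

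**4. Size of the bias in a contrast.** Assumed: last-value dropout, 100 per group (400 / 4), no true difference, available-case estimates.
- 15% versus 25% loss: false contrast 0.03-0.07 SD. Pairwise SE = sqrt(1/75 + 1/85) = 0.158. At the upper end 0.07 / 0.158 = 0.44, so a two-sided 5% test rejects about 7% (simulated range 5.4-7.2%).
- Obesity by onset interaction, one cell at 25% and three at 15%: same bias, SE = sqrt(1/75 + 3/85) = 0.221, 0.07 / 0.221 = 0.32, rejection about 6% (range 5.2-6.2%).
- 10% versus 30% loss, a more extreme case: 0.06-0.13 SD; rejection 6.3-13.4% pairwise and about 5.9-9.2% for the interaction.
- Equal 20% loss, same mechanism: 0.00 SD, rejection about 5%.
- Loss equally higher in both obese groups, same mechanism: the biases cancel in the interaction.

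If dropout follows the unseen value, maximum likelihood still leaves a contrast bias of 0.02-0.04 SD (15% versus 25%) or 0.03-0.08 SD (10% versus 30%).

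**5. What a shift analysis would show.** A group mean moves by loss fraction x shift: 0.20 x 0.5 SD = 0.10 SD. Opposite 0.5 SD shifts in two groups, even at equal 20% loss, move their contrast by 0.20 SD. Example: for an observed contrast of 0.40 SD with 80 observed per group, SE = sqrt(2/80) = 0.158 and the critical value is 1.96 x 0.158 = 0.31. Significance is lost once the lost patients in one group differ by (0.40 - 0.31) / 0.20 = 0.45 SD.

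**6. The biomarker-morbidity coefficient.** With an assumed true value of 0.30, dropout on the outcome and 20% loss, the estimate is 0.27-0.30. The false group difference is at most 0.02, even at 10% versus 30% loss.

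**The case against.** The strongest case on the other side has five parts.

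- **The hypothesised term is less exposed.** The SAP's Aim 1 hypothesis is carried by an obesity by onset interaction, not by a pairwise contrast, and its false-positive rate rises less. This stands, and both rates are given above.
- **The direct effects are adjusted.** They are estimated alongside the biomarker pathway and several covariates. No contrast was computed with covariates or mediator in the model, so the contrast figures are for unadjusted comparisons. This stands as a limit on the size, not on the gap.
- **The larger figures assume WLSMV on available data.** The SAP does not say this. Under maximum likelihood with last-value dropout the bias is zero. But the SAP itself declines missing at random, and with unseen-value dropout some bias remains under maximum likelihood.
- **The supplied text looks like an extract.** It refers to material above that is not included, so the absence of a method can be asserted only for the text supplied.
- **A large grid of scenarios would be out of proportion.** This stands; a compact one is enough.

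A reader might infer more: that the central relationship of Aim 1 ("Compare the longitudinal relationship between L-arginine/ADMA balance and morbidity"), mediation or Aim 2 is biased, or that lost patients' earlier visits are thrown away. The material does not support this. Step 6 shows little effect on the first; no effect was computed for mediation or Aim 2; and the Protocol retains collected data by default.

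**Conclusion.** The concern holds in a limited form. The SAP rejects missing at random for FEV1 and ACQ, yet in the supplied text outcomes after permanent loss have no committed handling and no sensitivity analysis for data not missing at random. Late-visit means and slopes can be biased if dropout depends on the outcome, by roughly 0.05-0.15 SD at 20% loss if estimates are available-case. Group contrasts are biased only if loss differs in rate or mechanism: about 0.03-0.07 SD at 15% versus 25%, which raises a 5% test to at most about 7% (pairwise) or 6% (interaction). All of these sizes rest on assumed dropout mechanisms and assumed loss by group. The effect on error rates is modest and the repair is inexpensive, so this is a cheap improvement rather than a flaw that threatens the study.

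**What to change.** (a) In the SAP's Missing Data section, replace the conditional sentence with a commitment to a compact pattern-mixture or delta-shifted sensitivity analysis of the FEV1 and ACQ growth models that includes permanently lost patients. Use a few shifts in both directions, allowed to differ by obesity/onset group. A range of -0.5 to +0.5 SD is illustrative: it covers the 0.02-0.07 SD left under maximum likelihood, which at 20% loss means lost patients differing by 0.10-0.35 SD (0.02 / 0.20 to 0.07 / 0.20) from prediction. The team should justify its own range. Report the shift at which each primary conclusion changes, including the obesity by onset interaction.

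(b) For the continuous FEV1 and ACQ models, use robust full-information maximum likelihood, at least as a comparison with WLSMV, so that earlier observed visits inform later means. It assumes missing at random, so (a) is still needed.

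(c) Report loss per visit by group, and extend the planned comparison of those lost to last observed FEV1 and ACQ.

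Cost: revised SAP wording, extra scripted model runs, and a somewhat more complex presentation with two estimators side by side. No new data, visits or patients.

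### Aims 1 and 2: the power method concerns overall model fit, but the result is stated for an undefined average effect, and the interaction and indirect effects that carry the aims have no power figure

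*SAP*

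**What the plan says.** All of the power text for Aims 1 and 2 is in the SAP paragraph headed Power Calculation.

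- Method: "Power calculations for LGCM and sample size based were based on published methods". No method is named.
- Effect size: "Effect size in this approach is defined as a null and alternative hypothesis value of the RMSEA index", with 0.05 as the null value and 0.03 as the alternative.
- Sample: "The estimated power is based on a proposed sample size of 400 with an 80% follow-up rate". Whether 400 or 320 entered the calculation is not stated.
- Aim 1 (14 latent and 34 observed variables): "yielding estimated power >0.80 for an average effect of 0.10 with an alpha of 0.05".
- Aim 2 (13 latent variables): "and 18 observed variables, yielding >0.80 power for average effects of 0.15".
- Conclusion, after a remark that power for such models is hard to estimate in advance: "we believe the proposed study will be adequately powered to address the research aims".

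The tests themselves are described elsewhere. Under Aim 1 the SAP expects the nitric oxide pathway to matter mainly in obese patients with late onset, and for that reason "we will include an interaction term between obesity and age of asthma onset". It fits direct and indirect effects, compares models with and without the direct effects, and reports effect sizes "along with Sobel tests and Monte Carlo confidence intervals to evaluate the mediational hypotheses". Under Aim 2 it carries the direct, indirect and mediation analyses over from Aim 1.

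**The concern.** The paragraph changes the quantity being powered. A test of RMSEA 0.05 against 0.03 asks whether the whole model fits closely. Its power is the same whether the paths are 0.10, 0.30 or zero, so it cannot by itself yield power for an average effect of any size. A separate calculation may exist, but nothing in the text shows one.

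The tests that will answer the aims are the interaction and the indirect effects, and neither has a power figure. A null result on either would be read against the SAP's assurance of adequate power.

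For mediation, the SAP lists the Sobel test and the Monte Carlo interval without saying which decides. The two can disagree on the same data.

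**Working it through.** **Inputs.** From the SAP's Power Calculation: 400 enrolled, 80% followed up (400 × 0.80 = 320), alpha 0.05, RMSEA 0.05 and 0.03, 34 and 18 observed variables. From SAP Aim 1: four visits. Assumed, because not stated: two-sided tests, within-person correlation 0.5–0.9, complete data, no covariates.

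**1. The stated method, RMSEA power.** With noncentrality λ = (N − 1) × df × RMSEA², power is the probability that a noncentral chi-square with λ(0.03) falls below the 5th percentile of one with λ(0.05). At N = 320 and df = 99:

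- λ(0.05) = 319 × 99 × 0.0025 = 78.95
- λ(0.03) = 319 × 99 × 0.0009 = 28.42
- power = 0.803 (0.799 at df 98)

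So 0.80 needs df ≥ 99 at N = 320, or df ≥ 71 at N = 400. The available moments, p(p + 1)/2 + p, are 629 for 34 variables and 189 for 18. Aim 2 reaches df 99 with up to 189 − 99 = 90 free parameters. More than 0.80 is thus attainable as model-fit power, but cannot be confirmed without the df.

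**2. The stated result, read as a time-invariant standardised path.** Power = Φ(atanh(r) × √(Nₑ − 3) − 1.96), where Nₑ = 4N/(1 + 3ρ) over four visits with within-person correlation ρ, and Nₑ = N at one visit.

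For r = 0.10 and N = 320:

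- one visit: 0.1003 × √317 = 1.786, power 0.43
- four visits, ρ = 0.9: Nₑ = 345.9, power 0.46
- four visits, ρ = 0.5: Nₑ = 512, power 0.62

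| Path | N = 320, one visit | N = 320, four visits | N = 400, one visit | N = 400, four visits |
|---|---|---|---|---|
| 0.10 | 0.43 | 0.46–0.62 | 0.52 | 0.55–0.72 |
| 0.15 | 0.77 | 0.80–0.93 | 0.85 | 0.88–0.97 |

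The interaction is a term of this kind. Take four equal cells of 80, in line with the balance expected in the protocol's Recruitment Methods. A standardised product path of 0.10 is then a difference of differences of 4 × 0.10 = 0.40 SD. At one visit its standard error is √(4/80) = 0.224 SD, so z = 1.79 and power is again 0.43.

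**3. Time-varying path of 0.10 at N = 320.** Information is N × [3(1 − rₓ)/(1 − rₑ) + (1 + 3rₓ)/(1 + 3rₑ)], where rₓ and rₑ are the predictor and residual within-person correlations.

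- Equal correlations: information 1,280, z = 0.10 × √(1,280/0.99) = 3.60, power 0.95.
- rₓ = 0.9, rₑ = 0.5: information 665.6, z = 2.59, power 0.74.

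Over 0.5–0.9, power falls below 0.80 (to 0.74–0.76) only when rₓ = 0.9 and rₑ = 0.5–0.7.

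**4. Other scales for 0.10 at N = 320.** As a standardised mean difference between two equal groups, power is 14%. As f² or R², it is above 99%.

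**5. Indirect effects over four visits at N = 320 (simulated illustration).** The model has a time-invariant cause, a time-varying mediator and outcome, no direct effect, equal within-person correlations of 0.5–0.9 and generalised least squares. Sobel rejects when |ab|/√(a²s_b² + b²s_a²) > 1.96. The Monte Carlo test rejects when the 95% interval from normal draws of a and b excludes zero.

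| Both paths | Sobel | Monte Carlo interval | Tests disagree |
|---|---|---|---|
| 0.10 | 26–41% | 41–57% | 15–17% |
| 0.15 | 77–90% | 82–93% | 3–5% |

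These are approximate. A separate run of 1,200 data sets per setting put the lower ends of the second row at 74% and 80%.

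**The case against.** The strongest reply is that more than 0.80 has not been shown to be wrong, and that stands. It is attainable as model-fit power, about right for a path of 0.15, met by most time-varying paths of 0.10, and comfortably met if 0.10 is an f² or R². The SAP also concedes the difficulty and words its conclusion as a belief. The model diagrams and the published methods could not be seen, so some of the missing detail may lie there. None of this supplies power for the interaction or the indirect effects.

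Three stronger readings are tempting, and the documents do not support them:

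- A reader might infer that the study is underpowered for its aims. That depends on an effect scale the SAP does not define.
- A reader might infer that mediation is badly underpowered at 0.15, with the two tests disagreeing in one data set in five. Those figures (35% Sobel against 56% Monte Carlo) arise only if mediator and outcome are measured once. The SAP plans four visits.
- A reader might infer that listing two mediation tests inflates false positives. Sobel is the conservative one. In a single-occasion simulation with the first path zero, false-positive rates were 0.3–3.7% for Sobel and 1.7–5.5% for the Monte Carlo interval. What is at stake is lost power and an undecided result.

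**Conclusion.** The point holds as a mismatch between method and result: the SAP describes power for overall fit, reports power for an effect with no scale, and draws a conclusion about aims whose main tests were not powered.

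The shortfall is specific. A time-invariant standardised path of 0.10, the interaction included, has 0.43–0.62 power at N = 320 and 0.52–0.72 at N = 400. Two such paths in sequence have at most about 57% at N = 320. At 0.15 there is no material shortfall: 0.77–0.93 for a single path, and roughly 80% or more for the indirect effect with the Monte Carlo interval.

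The mismatch and the missing power figures rest on the text alone. The sizes rest on the assumed correlations, two-sided testing, complete data and simple models without covariates or measurement error. They are illustrations and should not be copied into the SAP as detectable effects. This should be fixed, but it does not invalidate the design.

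**What to change.** 1. Label the RMSEA result as power for overall model fit only, and state the degrees of freedom for each aim.
2. Replace the two average-effect statements with Monte Carlo power, in the planned growth model, for the obesity-by-onset interaction and the indirect effects. Limit the sentence on adequate power to what that simulation shows. Simulate 400 enrolled with dropout to 80% by 18 months. Starting from 320 and adding missing data would count dropout twice. State the effect metric, cell sizes and within-person correlations, and report time-invariant and time-varying predictors separately.
3. Add to Aim 1, and apply to Aim 2:

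> An indirect effect is concluded only if its 95% Monte Carlo confidence interval excludes zero. The Sobel test is descriptive, and the constrained vs unconstrained comparison is used only to describe complete vs partial mediation once an indirect effect is shown.

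The cost is SAP wording and one simulation, with no extra patients or visits. The downside is that the stated power may become less favourable.

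An optional reporting note, separate from this point: the pilot's power statement in Aim 3 would be easier to check if the assumed standard deviations of its four instruments were given.
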